3.2 Study Endpoints

3.2.1 Primary Study Endpoints

The first primary effectiveness outcome is treatment response, a dichotomous indicator of whether a patient has achieved clear/almost clear skin (score of 0 or 1), based on the Physician's Global Assessment (PGA) at the earlier of week 12 or discontinuation of phototherapy. See Appendix B for PGA tool.

The second co-primary outcome is the patient-reported Dermatology Life Quality Index (DLQI) at week 12. We will dichotomize DLQI at a score of 0-5 (corresponding to no to small impact on quality of life) versus a score $\ge 6^{44}$.

3.2.2 Secondary Study Endpoints

- DLQI score of ≤1 (no impact on HrQOL)
- Achievement of a Minimal Clinically Important Difference (MCID) on the DLQI
- Concomitant topical psoriasis treatment
- Concomitant oral and biologic psoriasis treatment
- Patient reported time spent on phototherapy
- Patient reported time and cost associated with travel for phototherapy treatments
- Change in the product of BSA times PGA relative to baseline (BSAxPGA). See Appendix B for BSA tool.
- Duration of treatment response during observation period
- Phototherapy number and dose

3.2.3 Primary Safety Endpoints

The primary safety outcome is the proportion of patients reporting treatment-emergent adverse events. Adverse events include patient reported burns and their severity. Patients will be queried about these events immediately prior to each phototherapy treatment by the clinical staff (for patients assigned to office base phototherapy) or by the home phototherapy machine. We will also evaluate all serious adverse events regardless of their relationship to treatment. All patients will be queried about SAEs by the sites at the visit 2. Patients can spontaneously report SAEs at any point during the study.

4 Study Population and Duration of Participation

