6.2.2 Weeks 2,3,5,6,7,9,10,11

- Administer NB-UVB phototherapy three times per week
- Patient reported response to phototherapy prior to treatments. For those on office treatment, data is entered by the sites. For those on home treatment, data is recorded on the home device.
- Phototherapy session number and dose. For those on office treatment, data is entered by the sites. For those on home treatment, data is recorded on the home device.

6.2.3 Weeks 4 & 8

- Administer NB-UVB phototherapy three times per week
- Patient reported response to phototherapy prior to treatments. For those on office treatment, data is entered by the sites. For those on home treatment, data is recorded on the home device.
- Phototherapy session number and dose. For those on office treatment, data is entered by the sites. For those on home treatment, data is recorded on the home device.
- Patient reported DLQI
- Patient reported target lesion image
- Patient reported psoriasis topical treatment

6.2.4 Week 12

- Administer NB-UVB phototherapy three times per week
- Patient reported response to phototherapy prior to treatments. For those on office treatment, data is entered by the sites. For those on home treatment, data is recorded on the home device.
- Phototherapy session number and dose. For those on office treatment, data is entered by the sites. For those on home treatment, data is recorded on the home device.
- Site reported concomitant oral and biologic psoriasis medications

6.2.5 End of Treatment/ Visit 2 (occurs at Week 12 (plus or minus 2 weeks) or at time that patient discontinues phototherapy, whichever comes first)

- Clinician measured PGA score
- Clinician measured BSA assessment
- Patient reported DLQI
- Patient reported time spent on travel, cost of travel, and time spent on phototherapy (administered by site)
- Patient reported target lesion image
- Site reported concomitant oral and biologic psoriasis medications
- SAE Assessment

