6.5.1 Data Collection and Follow-up for Withdrawn or Early Termination Participants

Participants who withdraw consent to participate in the study will be asked to report the reason for withdrawal.

7 Study Evaluations and Measurements

The data collected in this study are all considered relevant for routine clinical care. In routine clinical care, there is some variation in which assessments are conducted and thus we will standardize assessments for the purpose of the study.

Investigator reported measures:

1. Physicians Global assessment (PGA): This is a three item measure that asks the physician or his or her designee to assess the thickness, redness, and scale of psoriasis plaques.

2. Body Surface Area (BSA): This is a measure that asks the physician or his or her designee to assess the body surface area affected by psoriasis using the handprint method in which the palm of the entire hand approximates 1% of the body surface area. To do this, the patient's handprint, including the entire area of the palm and all 5 digits with the fingers close together but not overlapping, is used as a guide to estimate 1% of the BSA

3. Number of phototherapy treatments and dose received: This data is routinely collected in clinical practice. It will be reported by the sites for patients receiving office treatment and will be obtained from the machines for those receiving home based treatment

- 4. Copay for office-based phototherapy
- 5. Concomitant treatment

Patient reported measures:

1. Dermatology Life Quality Index: (DLQI): DLQI is a 10 item survey that asks patients questions about their health related quality of life on a 0-3 scale. DLQI is routinely used in clinical trials of psoriasis treatments and can also be used routinely in clinical practice.

2. Patient reported response to phototherapy: This is a standard question asked to the patient to document the degree and duration of erythema induced by the prior phototherapy treatment session. It is standard of care.

- 3. Patient reported time spent on travel, cost of travel, and time spent on phototherapy
- 4. Patient reported concomitant psoriasis topical treatment

5. Photograph of target psoriasis lesion (at a subset of study sites)

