7.2 Physical Examination

A complete examination of the skin will be conducted at visit 1 and 2 as well as at any unscheduled visits if deemed necessary by the patient's clinician. A physician global assessment and body surface area affected by psoriasis will be reported from the physical examination.

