7.6 Safety Evaluations

Safety will be monitored by the local clinicians.

Patients will be queried about the reaction to phototherapy (i.e., burns) immediately prior to each phototherapy treatment as is standard practice. Patients will contact the study clinicians for any significant reaction to phototherapy (a burn which requires medical attention such as one associated with significant pain that interrupts usual activities or skin blistering). Patients will be queried about SAE's at visit 2. Patients can spontaneously report SAEs at any point during the study.

8 Statistical Plan

8.1 **Primary Endpoint**

Primary analyses will be based on the intent to treat (ITT) population defined as all patients meeting eligibility requirements who are randomized to one of the two study arms. In the ITT population, we will compare the two treatment arms with respect to two primary effectiveness outcomes. The first primary effectiveness outcome is treatment response, a dichotomous indicator of whether a patient has achieved clear/almost clear skin (score of 0 or 1), based on the Physician's Global Assessment (PGA) at the earlier of week 12 (visit 2), defined as the twelfth week after the start of treatment, or the time of discontinuation of phototherapy. In our primary analyses, patients who drop out of the study prior to achieving clear/almost clear skin or week 12, whichever comes first, will be classified as treatment failures (i.e., failure to achieve clear/almost clear skin). The second primary outcome is the patient-reported Dermatology Life Quality Index (DLQI) assessed at week 12. We will dichotomize DLQI at a score of 0-5 (corresponding to no to small impact on quality of life) versus a score >5. Patients failing to complete the week 12 DLQI assessment will be assumed to have DLQI >5 and therefore classified as a non-responder on this measure.

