8.4.3 Safety Analysis

The primary safety outcome is the proportion of patients reporting treatment-emergent adverse events. Adverse events include patient reported burns and their severity. We hypothesize that safety of home based UVB phototherapy will not be different from office based phototherapy. We anticipate based on extensive experience, that the number of clinically significant burns (i.e., which may require the patient to seek advice from the treating physician and occur due to human error) will be rare (affecting <1% of patients) and typically can be managed at home with over the counter remedies.

As ultraviolet light does not have adverse effects beyond the skin, our stakeholders believe that safety assessments should focus on skin related events such as burns and serious adverse events. We will summarize the number, severity, and type of adverse events experienced by patients in each treatment arm. We will compute the proportion of patients experiencing adverse events by treatment arm, with 95% CI. Similar to analyses for our effectiveness outcomes, we will also fit skin type-adjusted logistic regression models and use standardization to estimate adjusted risk differences between treatment arms. In addition to pooled safety analyses, we will also compare the proportion of patients experiencing adverse events between office-based and home-based phototherapy arms within each skin type sub-group

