9.2 Recording of Adverse Events

This pragmatic trial will be evaluating the effectiveness of two standard of care treatments, home and office-based phototherapy. All treatments will be administered and monitored by the patient's clinical care provider (dermatologist) and designated staff (typically phototherapy nurses). Recording of reported adverse events will be completed by the patient's clinical care provider(s) prior to the administration of each treatment (3 times per week) and the clinical course of each event will be followed until resolution, stabilization, or until it is determined that phototherapy is not the cause. Adverse events will be documented in the patient's medical record by the clinical care provider(s) throughout the 12 week intervention period and the subsequent 12 week observation period per local practice or medical center requirements. Only phototherapy-emergent adverse events will be abstracted from medical records and/or home phototherapy equipment and recorded for study objective purposes.

Serious adverse events will be recorded and monitored by the patient's clinical care provider(s), per standard of care practices, and will also be recorded, tracked, and reported by the study in the appropriate case report form and SAE reporting form at Visit 2. Serious adverse events that are identified at the end of the study intervention period will be followed up to determine the final outcome. Any serious adverse event that occurs after the study intervention period and is considered to be possibly related to the study intervention or study participation will be recorded and reported immediately.

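### Burns are asked about only before the next treatment, so a non-serious burn after a patient's last session has no scheduled question in either arm

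*Combined protocol and SAP*

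**What the plan says.** Sections 3.2.3 and 8.4.3 define the primary safety outcome as the proportion of patients with treatment-emergent adverse events. Patient-reported burns and their severity are included, with no minimum severity.

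**When burns are asked about.** Section 3.2.3 places the query "immediately prior to each phototherapy treatment by the clinical staff (for patients assigned to office base phototherapy) or by the home phototherapy machine"; Section 7.6 gives the same timing. Section 7 (patient-reported measures, item 2) says the question serves to "document the degree and duration of erythema induced by the prior phototherapy treatment session". The lists for weeks 1 to 12 (6.2.1 to 6.2.4) repeat this pre-treatment item.

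**What happens at the end of treatment.** Visit 2 (6.2.5) takes place at week 12, plus or minus 2 weeks, "or at time that patient discontinues phototherapy, whichever comes first". Its list covers PGA, BSA, DLQI, travel and treatment time, a lesion image, oral and biologic medication, and an SAE assessment. Section 3.2.3 agrees: "All patients will be queried about SAEs by the sites at the visit 2". The lists for weeks 16, 20 and 24 (6.3.1) have no reaction item.

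**Other ways a burn can reach the data.**
- Section 7.6: "Patients will contact the study clinicians for any significant reaction to phototherapy".
- Section 7.2 requires a complete skin examination at Visit 2. On reporting, it says: "A physician global assessment and body surface area affected by psoriasis will be reported from the physical examination".
- The opening of Section 9 makes site staff responsible for reviewing reactions and identifying treatment-emergent events.
- Section 9.2 has events charted per local practice through the observation period, then: "Only phototherapy-emergent adverse events will be abstracted from medical records and/or home phototherapy equipment and recorded for study objective purposes".
- Section 6.5.1 asks patients who withdraw consent for their reason.

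**The concern.** A query placed before each treatment and looking back one session works for every session except the last. Over a full course this is a small omission. For a patient who stops early, the uncovered session is the one just before stopping, which is where a burn that ends treatment would fall. Such a burn is among the most informative events in a comparison of home with office treatment, yet unless it is serious the plan schedules no question about it.

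The safety comparison matters to the trial's purpose. Section 1.1 cites a review saying that doubt about the safety of home units has made prescribers reluctant to use them. A reader of the results will want to know that every patient was asked, at the end, whether they had been burned.

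**Working it through.** The plan gives no sample size, power or missing-event figure for the safety outcome, so there is no figure of its own to reproduce. The check is first a comparison of the visit lists, then a bound.

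**1. Which sessions are followed by a question.** The reaction to session k is asked about just before session k+1. With K sessions received, sessions 1 to K−1 are covered and session K is not.
- Full course, K = 36 (Section 5.7): 1/36 = 2.8% of sessions uncovered.
- Early stop: the uncovered session is the one immediately before stopping.
- K = 1: the patient is never asked about a reaction.

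**2. Whether a later list fills the gap.** Visit 2 (6.2.5) has an SAE assessment and no reaction item; weeks 16, 20 and 24 (6.3.1) have none. This reading rests on the body text. The contents of Appendices D and E were not available, but Section 7.4 says that all evaluations are described in the body.

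**3. How far the other routes reach.**
- Patient contact is expected only for significant reactions.
- The Visit 2 examination may show a recent burn, but only PGA and BSA are named as reported from it, and a healed burn will not be seen.
- Charting follows local practice. Section 8.4.3 says that clinically significant burns "typically can be managed at home with over the counter remedies", so some may leave no clinic record.
- The withdrawal question reaches those who withdraw consent, not everyone who merely stops phototherapy.

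**4. Bound for clinically significant burns.** Inputs: 1050 randomized 1:1 (Sections 3.1 and 4.5), so n = 1050/2 = 525 per arm; risk p below 1% (Section 8.4.3). If enrolment follows the strata in Section 3.1, n = (350 + 350 + 80)/2 = 390. Let f be the share of affected patients whose only burn follows the last session. The documents do not give f, so the values below are assumptions. Patients never asked = f × p × n, before any capture by the routes in step 3.

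| f (assumed) | n = 525 | n = 390 | points lost from the arm's rate |
|---|---|---|---|
| 10% | 0.53 | 0.39 | 0.1 |
| 50% | 2.63 | 1.95 | 0.5 |
| 100% | 5.25 | 3.9 | 1.0 |

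**5. Effect on the arm difference.** With equal true risk p, the observed home-minus-office difference is p(1 − f_home) − p(1 − f_office) = −p(f_home − f_office). If f is the same in both arms, this is zero. At p = 1%, f_home = 50% and f_office = 10%, it is −0.01 × 0.40 = −0.4 points. The extreme, 100% against 0%, is −1.0 point.

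**6. Milder burns.** The plan gives no expected rate for milder burns in this population. As illustration only, at an assumed 5% risk and f of 10%, 25% or 50%, the observed rate would be 4.5%, 3.75% or 2.5%. At an assumed 10% risk it would be 9%, 7.5% or 5%.

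**The case against.** The strongest reply is that this is deliberate, routine-care safety capture with several safeguards. Section 9 gives sites an assigned duty to review reactions and identify treatment-emergent events. For a patient who stops, Visit 2 falls at discontinuation and includes a full skin examination, so a clinician looks at the skin near the relevant time. Section 9.2 keeps charting open through the observation period, and Section 9.3 has the site investigator or a designee review all adverse events. The gap also exists in both arms, and nothing in the documents suggests that it is larger in one.

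Most of this stands, and it rules out saying that such burns go uncaptured. It does not supply the missing question: none of these provisions has anyone ask every patient, after the last session, whether they were burned.

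Three stronger readings are tempting, and the documents do not support them.
- *Home reaction answers are lost with unreturned devices.* Section 5.6 accepts that some devices will not come back, and Section 5.7 has treatments verified on return. Neither says that reaction answers are lost. Section 9 has sites reviewing reactions and adjusting doses, which suggests access during treatment. Office entries depend on site staff and can be missing too.
- *The lack of a missing-data rule for safety is an error.* Section 8.5 bases the primary analysis on all randomized patients, Section 8.4.3 models safety like effectiveness, and the tipping-point plan in Section 8.4.5 is not confined to effectiveness. What is absent is detail that analysts could fill.
- *The home rate could lie anywhere in a wide range.* If an assumed 10% lacked data and 1% of the rest had a burn, the limits would be 0.01 × 0.90 = 0.9% and 0.9% + 10% = 10.9%. The width only restates the assumed 10%.

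**Conclusion.** The point holds as a gap in how the primary safety outcome is collected. In both arms, a non-serious burn after the last session has no scheduled question and depends on partial routes. That includes a burn that caused the patient to stop.

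The effect on the arm difference cannot be estimated from the documents. For clinically significant burns it is at most 1 percentage point, and probably much smaller, because the gap applies to both arms and the other routes recover some events. This rests on the plan's expected rate of below 1%, equal true risk in the arms, and assumed values of f. The small bound does not cover the whole outcome, since milder burns count too and no rate is given for them. A reader might infer a bias in favour of home treatment; the documents do not support a direction.

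The gap does not invalidate the trial. It is worth closing because it falls on the burns that matter most to the safety question and costs little to close.

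**What to change.** At Visit 2, alongside the SAE query, have site staff ask every patient in both arms:
1. the degree and duration of any reaction to the last session;
2. whether any burn led to stopping phototherapy;
3. any burn since starting, with its worst severity.

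State in Section 8.4.3 that burns after the last session count in the primary safety outcome. Use the 12-week recall in item 3 only to supplement the per-session record, which stays as it is. This matters because recalled and real-time answers would otherwise be mixed, possibly unequally between arms.

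The cost is one short eCRF item at an existing visit and a small amendment across roughly 20 to 40 sites, some under local IRBs. Limits remain: recall of mild erythema is weak, patients who miss Visit 2 are not covered, and a Visit 2 held early in its window can precede the last session.

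As an optional clarification, separate from the gap itself, report by arm how many patients lack per-session reaction data, and say that the tipping-point analysis in Section 8.4.5 extends to the safety outcome.

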4.1 Inclusion Criteria

Inclusion criteria:

- 1. Willing and able to provide informed consent (age 18+) or parental permission and assent (ages 12-17)
- 2. Age 12 or older
- 3. Plaque or guttate psoriasis predominantly located on trunk and/or extremities, with a physician global assessment average of >1.0, and considered a candidate for phototherapy
- 4. Patient is deemed willing and able to comply with either in-office or in-home phototherapy:
 - a. In office: Able to travel about 3 times per week for 12 weeks from home, work and/or school during business hours of local site
 - b. In home: Has space to accommodate home phototherapy unit and patient (or if 12-17, parent), willing and able to follow home phototherapy instructions
- 5. New or established patient in the practice

4.2 Exclusion Criteria

Exclusion criteria:

- 1. Patients who are judged unable or unwilling to comply with either in office or in home phototherapy due to time, work, school, or other financial constraints
- 2. Patients judged unable to follow home phototherapy protocol due to failure to demonstrate understanding of the following:
 - a. How to operate the phototherapy device
 - b. How to follow the dosing protocol
 - c. Requirement to wear protective eyewear and genital protection equipment
- 3. Patients with known history of lack of efficacy to phototherapy or treated with phototherapy 14 days prior to baseline visit.
- 4. Psoriasis predominantly located on scalp, body folds, genitals, palms and/or soles or with a physician global assessment average of ≤ 1.0
- 5. Patients deemed unsafe to be treated with phototherapy:
 - a. History of photosensitivity or autoimmune disease such as lupus or dermatomyositis which can be aggravated by ultraviolet radiation
 - b. History of arsenic intake
 - c. Unable to tolerate standing for required duration of treatment due to age or physical function
 - d. History of melanoma or multiple non-melanoma skin cancers that in the opinion of the principal investigator contraindicates treatment with phototherapy
- 6. Clinical site deems the participant is ineligible for reason other than eligibility or screening criteria.

4.3 Subject Recruitment

Patients will be recruited from approximately 20-40 sites across the United States by dermatologists who offer office-based phototherapy. The patients will be recruited during routine clinical evaluation when the patient and physician (or appropriate provider such as physician assistant or nurse practitioner) are embarking on a course of treatment for plaque or guttate psoriasis.

4.4 Duration of Study Participation

The screening period is up to 28 days or longer based on the local practice standard of care. The total duration of participation after starting phototherapy is 168 days (i.e., intervention and observation periods). The total participation including the screening period is up to 196 days but could be longer as the screening period length will be determined by local standard of care.

